Appendix 4: StatinWISE Patient questionnaire

INSTRUCTIONS

This questionnaire is to be filled out once every two months (on day 56). We will remind you one day before it is due. Please answer all questions. If you need any help to complete the form. Please call our Freephone number [name] or email the study team: [contact].

PART 1: ADHERENCE TO MEDICATION

Step 1 (all participants):

Q1. How would you best describe your use of study medication in the past two months? (Please choose one of the following options)

- I didn't take my study medication at all
- I took my study medication on some days
- I took my study medication on most days, but missed an occasional dose
- I took my study medications every day

Step 2 (appears if the participant chooses "I didn't take my study medication at all", or "I took my study medication on some days"):

Q2. What was the reason that you didn't take your study medication every day in the past two months? (please tick all that apply)

- I forgot to take my study medication

Ticking the above will prompt the following option, if ticked, the trial team will action:

- Would you like a daily reminder sent to you via email/push notification

- I was prescribed another medication and my doctor told me to stop taking my study medication

Ticking the above will prompt an alert for the trial team to contact surgery for details and consider withdrawal from study

- My doctor recommended that I stop taking study medication because of muscle symptoms

Ticking the above will prompt an alert for the trial team to contact surgery for details

- I decided to stop taking study medication because of muscle symptoms

Ticking the above will prompt an alert for the patient to contact the GP for advice

- I didn't want to take my study medication

Ticking the above will prompt the following option, if ticked NO, the trial team will arrange for end of trial:

Do you still wish to participate in the trial: Yes No

- Other (please specify)

(free text)

PART 2: EXPLORING SYMPTOMS IN THE PAST TWO MONTHS

1. *(all participants):* In the last two months, have you experienced muscle symptoms, e.g. muscle pain or weakness?

Yes
 No

2. *(appears if the participant ticks yes for Question 1):* Do you think these muscle symptoms are related to your study medication?

Yes
 No
 Don't know

[figure not shown]
3. *(appears if the participant ticks no for Question 2):* What do you think may have caused these muscle symptoms?
(free text)

Don't know

[figure not shown]
4. *(appears if the participant ticks yes for Question 1):* Indicate with a cross (x) on the scale the number that describes how, during the last two months, pain has interfered with your:

- General activity
- Mood
- Walking ability
- Normal work (includes both work outside the home and housework)
- Relations with other people
- Sleep
- Enjoyment of life

For each of (a) to (g), the following scale will appear:

5. (appears if the participant ticks yes for Question 1): **On the diagram, tap to highlight the area that hurts the most.**
(Paper form will read: 'On the diagram, put an X on the area that hurts the most.')

More than one area

The body will be divided into the following locations and answers should be categorized depending where the participant taps. For paper forms, the location given by X marked on the body will be entered into the web or app version at data entry. Locations: head and neck/upper limbs/lower limbs/trunk.

6. (All participants): **In the last two months, have you experienced any other symptom that you think is associated with your study medication?**

Yes (please specify)
(free text)
 No
 Don't know

PART 3: ADVERSE EVENTS

1. (All participants): **Have you been admitted to hospital in the last two months?**

Yes
 No

[figure not shown]
[figure not shown]
2. (Appears if the participant ticks yes for Question 1): **What was the reason for your admission to hospital?**

[figure not shown]
[figure not shown]
[figure not shown]
[figure not shown]
(free text)

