2.10.3 END OF TRIAL DATA

During the seventh week of treatment period 6, the Research Nurse will contact patients to thank them for their participation so far, inform them that this is the last treatment period, and that they, together with their GP, will receive their individual results at the beginning of month 14. The Research Nurse and patient will arrange a telephone or face-to-face appointment to discuss the individual results during month 14. The Research Nurse will also inform patients that if they want to continue taking a statin without a break, to arrange a separate clinical appointment with their GP prior to the end of the treatment period.

At month 15, trial staff will email/telephone the patient to document their decision on future statin use and whether their results helped reach this decision. This will be the last data collection point of the trial.

Throughout the trial, continued patient care will be at the discretion of their GP. In primary care, the patient will be recorded as having an ongoing statin prescription.

- Where treatment with an interacting drug is needed that will be for less than one-month duration, the patient will be asked to stop the trial treatment for that period.
- Where treatment with an interacting drug is needed for longer than one month, the patient will be asked to withdraw from study treatment completely.

When the patient is randomised, a temporary Read code indicating StatinWISE participation will be recorded in their primary care record, the code will be removed at the end of the trial.

Patients will also be given an alert card that identifies them as a StatinWISE patient. Patients will be asked to present this card to anyone providing medical care outside of their usual general practice. This card will have a link to the trial website and a trial contact number.

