2.13 OUTCOME MEASURES

Primary outcome: The primary outcome is self-reported 'muscle symptoms', defined as pain, weakness, tenderness, stiffness or cramp to the body of any intensity, recorded where the participant believes they are associated with the study medication; these are the symptoms most commonly reported by patients and are often the reasons for discontinuation. The primary outcome will be assessed by the mean difference in VAS scores (range 0 to 100) between treatment periods with the trial treatment and treatment periods with placebo, estimated via a linear mixed model.

Secondary outcomes: Secondary outcomes relating to participant belief about the cause of their muscle symptoms, the site of muscle symptoms, how the muscle symptoms affected the participant and information about any other symptoms will be collected on the last day of each two-month treatment period, using a questionnaire (Appendix 5). The other secondary outcomes are adherence

to medication, the participant's decision about statin treatment following the trial, and whether they found their own trial result helpful.

Specifically, secondary outcomes will be:

1. The proportion of patients with muscle symptoms during each two-month period who report that they believe their symptoms were caused by the study medication, comparing periods of IMP treatment with placebo.
2. Site of muscle symptoms (single or multiple; head and neck/upper limbs/lower limbs/trunk).
3. Among patients reporting muscle symptoms, the difference in mean VAS scores (range 0 to 100) for the following, comparing periods of IMP treatment with placebo:
 - a. General activity
 - b. Mood
 - c. Walking ability
 - d. Normal work (includes both work outside the home and housework)
 - e. Relations with other people
 - f. Sleep
 - g. Enjoyment of life
4. Other symptoms that the patient believes can be attributed to the study medication (grouped: musculoskeletal; gastrointestinal; respiratory; neurological; psychological; other).
5. Adherence to study medication as assessed by: (a) self-report and (b) counting pills remaining in returned packages, and the relationship between adherence and muscle symptoms.
6. Participant decision regarding future statin use and the relationship to their primary outcome.
7. Whether patients found their own trial result helpful in making the decision about future statin use.

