Appendix 3: StatinWISE End of Trial data form

End of Trial Form (Month 15) / Early Withdrawal

1. Did the patient complete 6 Treatment Periods?

YES

A.1. Has the Research Nurse/GP spoken to the patient to discuss their individual results?

(i) YES

(ia) Date seen: _____ dd/mm/yyyy

(ii) NO – (please arrange an appointment).

(iia) Date of appointment: _____ dd/mm/yyyy

A.2. Has the patient seen his/her GP since end of Treatment Period 6?

(i) YES

(ii) NO (please remind the patient to book an appointment)

(iia) Date reminder done: _____ dd/mm/yyyy

A.3. Has the patient been given a statin prescription in the 4 weeks since Treatment Period 6 ended?

(i) YES

(ia) Name of Statin: _____

(ib) Dose of statin: _____

(ii) NO

A.4. Has the patient found their own trial results helpful to reach the decision as to whether to continue statin use?

YES/NO

NO

B.1. Please tick reason why the patient did not complete 6 treatment periods:

Lost to follow-up

Early withdrawal

Death

B.2. Lost to follow-up:

Date of last contact with patient? _____

Dd/mm/yyyy

B.3. If Early withdrawal, give reason:

- a. withdrawal of informed consent
- b. intolerable muscle symptoms*
- c. clinical concern*
- d. other*

*: please enter details here: _____

B.4. Has the patient contacted their GP to discuss reason for withdrawal?

(i) YES

(ia) Date seen: _____ dd/mm/yyyy

(ii) NO – (advise patient to contact GP).

B.5. Has the Research Nurse/GP spoken to the patient to discuss their individual results?

(i) YES

(ia) Date seen: _____ dd/mm/yyyy

(ii) NO – (please arrange an appointment).

(iia) Date of appointment: _____ dd/mm/yyyy

B.6. Death (SAE report form must be completed)

B.6.a. Date of death: _____ dd/mm/yyyy

B.6.b Cause of death (either autopsy report or clinical judgement if autopsy not available):

B.6.c. Date SAE form completed: _____ dd/mm/yyyy

C.1. This form was completed by: _____ Date: dd/mm/yyyy

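### The question asking why doses were missed is not shown to patients who answer 'most days', so the reason for a late or short stop may not reach the trial database

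*Protocol*

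**What the plan says.** Part 1 of the Patient Questionnaire (Protocol, Appendix 4) first asks every participant to choose one of four descriptions of use: not at all, some days, most days, or every day. The third reads in full "I took my study medication on most days, but missed an occasional dose". Step 2 then asks "What was the reason that you didn't take your study medication every day in the past two months", but this question "appears if the participant chooses 'I didn't take my study medication at all', or 'I took my study medication on some days".

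The reasons offered in Step 2 include "I decided to stop taking study medication because of muscle symptoms", a parallel option for a doctor's recommendation to stop because of muscle symptoms, and "I was prescribed another medication and my doctor told me to stop taking my study medication". Each of these triggers an alert: to the trial team to contact the surgery, or to the patient to contact the GP. The 'forgot' option triggers an offer of a daily reminder.

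Section 2.13 of the protocol makes adherence, and "the relationship between adherence and muscle symptoms", the fifth secondary outcome. Section 2.10.3 provides for interruptions by design: when an interacting drug is needed for less than a month, "the patient will be asked to stop the trial treatment for that period". Section 2.10 limits the trial database to what is on the baseline, follow-up, end-of-trial and adverse-event forms.

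**The concern.** The display rule does not match the question. The question is about not taking medication every day, but one of the three answers that mean exactly that does not open it. Every structured option naming muscle symptoms or another drug as the cause of a stop lies behind this rule.

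The patients most likely to be missed stopped late in a period, or stopped briefly and restarted, because they can truthfully say they took capsules on most days. Late stops fall in or just before the eighth week, when the daily symptom scores are collected. For secondary outcome 5 the reason matters. If lower adherence goes with more symptoms, the analyst will want to know whether symptoms led to the missed doses or the doses were forgotten. The alerts are also at stake: they cannot fire for a patient who never sees the question.

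**Working it through.** The plan states no figure on this point, so there is none to reproduce. The check has two parts: which stops could be answered 'most days', and what else on the forms would record the reason.

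**Share of days taken.** Period length is 56 days (SAP 2.3.1). For a stop of d days, the share taken is (56 − d)/56.

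| Days missed | Days taken | Share |
|---|---|---|
| 7 | 49 | 49/56 = 87.5% |
| 14 | 42 | 42/56 = 75.0% |
| 27 | 29 | 29/56 = 51.8% |
| 28 | 28 | 28/56 = 50.0% |

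A single stop of up to 27 days therefore leaves a majority of days taken. I read the interacting-drug rule in section 2.10.3 as a stop for as long as that drug is needed. With a month counted as 28 days, every such stop (27 days at most) leaves a majority. With 30 days, the longest (29 days) leaves 27/56 = 48.2%, so nearly all do. If the rule instead means the rest of the treatment period, some stops would be longer and the reason question more likely to open.

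**What the daily form sees.** The form (Appendix 5) covers the last seven days of the period and asks about the previous day's dose. Assuming it is completed on days 50 to 56, it covers the doses of days 49 to 55.

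- Stop over the last 7 days: doses 50 to 56 missed, 50 to 55 seen, so 6 of 7.
- Stop over the last 14 days: doses 43 to 56 missed, 49 to 55 seen, so 7 of 14.

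**Where the reason could be recorded.**

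| Source | Records missed doses? | Records the reason? |
|---|---|---|
| Adherence question (Appendix 4, Part 1, Step 1) | Four categories, no day counts | No |
| Reason question (Step 2) | No date or count | Yes, but only after 'not at all' or 'some days' |
| Daily form (Appendix 5) | Yes, last week only | No |
| Pill count (SAP 1.8, range 0 to 56) | A total, if packs are returned | No |
| Report to the study team on stopping (Protocol 2.10.4) | Patient informs the team | Symptoms are reported, but no form is shown for it |
| End of Trial form (Appendix 3, B.3) | No | Only for early withdrawal from the trial |

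For a temporary stop answered 'most days', no row supplies a recorded reason. Given the limit on the database in section 2.10, a conversation with the study team does not fill the gap.

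**A related, smaller gap.** In Appendix 3, item B.3 lists "withdrawal of informed consent" beside intolerable muscle symptoms, clinical concern and other. The last three carry an asterisk asking for details and the first does not. A patient who withdraws consent because of symptoms could be entered under the first alone, with no prompt to say why. SAP 2.3.7 plans to summarise reasons for withdrawal.

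**The case against.** The strongest reply is that little is lost. The missed doses have two planned measurements, the daily form and the pill count. Patients who stop temporarily or permanently are asked to tell the study team and report symptoms at that time. Part 2 of the questionnaire asks every participant, whatever the adherence answer, about muscle symptoms and, if present, whether they relate them to the study medication. The daily form sets the previous day's dose beside that day's symptoms. Off-drug days in the scoring week can therefore be identified and compared with symptoms and attribution. All of this stands. What is missing is the patient's stated motive for stopping.

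The reply continues that a block of 7 or 14 missed days is hardly an occasional dose, so such a patient may well choose 'some days' and be asked. That also stands. The options have no day counts, and the documents do not say how patients would choose. It makes the loss uncertain but does not remove it.

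A reader might go further and infer that these stops go unrecorded, that the muscle-symptom reason is never offered to late stoppers, or that a statin–placebo difference in symptom-driven stopping would be missed for lack of power. The documents support none of these. The first two fail for the reasons just given. On the third, the SAP plans no comparison of reasons for missed doses. Section 2.3.7 compares adherence and the period of withdrawal between treatments and adds an instrumental-variables analysis, all built on adherence measures or withdrawal timing. A power figure would rest on invented stopping rates for an unplanned test.

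On B.3, the form carries no single-choice instruction, so two reasons could be marked. Miscoding there is possible, not shown.

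**Conclusion.** The point holds in a limited form. The display rule is narrower than the question it controls. For patients who stop late or briefly and answer 'most days', the reason may not reach the database, and the alerts tied to muscle symptoms or another medication do not fire. The share of days taken makes that answer plausible for stops of one to two weeks and for nearly all interacting-drug stops of under a month. How often it would be chosen is unknown, so the number of affected periods cannot be given.

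The consequence is for interpretation: the description of adherence and its link with symptoms. SAP 1.10 compares periods by allocation regardless of adherence, so neither the primary estimate nor its test uses the reason. This is a minor gap, worth closing because closing it is nearly free and the reason is hard to reconstruct later. The conclusion assumes that the forms listed in the protocol are the complete set.

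**What to change.** Show the reason question to everyone who does not tick 'every day'. This brings the display rule into line with the question's own wording and leaves the options and alerts as they are. It costs one branching condition and one extra tick-box question for patients who missed a few doses. More alerts and reminder offers would follow, with some added work for the trial team. The change does not date a stop. The daily form does that for the last week only, so a date field would be needed if earlier timing is wanted.

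Optionally, in Appendix 3, item B.3, ask for details under the consent-withdrawal option as for the other three, or state that more than one reason may be marked. Either lets symptom-driven consent withdrawals be identified, at the cost of one form item.

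For periods already completed on the present form, the SAP should say that reasons for missed doses are available only for the two lowest adherence categories.

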Appendix 5: StatinWISE VAS Pain Scale data form

You will be asked to complete this form each day during the last seven days of each two-month treatment period.

Day	Daily symptoms report		
1	1. Did you take study medication yesterday? No  Yes 	2. Did you experience muscle symptoms today? No  Yes  If yes:	3: Please indicate severity of muscle symptoms you experienced today.  0 No symptoms 5 Moderate symptoms 10 Worst possible symptoms
2	1. Did you take study medication yesterday? No  Yes 	2. Did you experience muscle symptoms today? No  Yes  If yes:	3: Please indicate severity of muscle symptoms you experienced today.  0 No symptoms 5 Moderate symptoms 10 Worst possible symptoms
3	1. Did you take study medication yesterday? No  Yes 	2. Did you experience muscle symptoms today? No  Yes  If yes:	3: Please indicate severity of muscle symptoms you experienced today.  0 No symptoms 5 Moderate symptoms 10 Worst possible symptoms

4	
1. Did you take study medication yesterday? No  Yes 
 
2. Did you experience muscle symptoms today? No  Yes  If yes:
 
3: Please indicate severity of muscle symptoms you experienced today.
 
5	
1. Did you take study medication yesterday? No  Yes 
 
2. Did you experience muscle symptoms today? No  Yes  If yes:
 
3: Please indicate severity of muscle symptoms you experienced today.
 
6	
1. Did you take study medication yesterday? No  Yes 
 
2. Did you experience muscle symptoms today? No  Yes  If yes:
 
3: Please indicate severity of muscle symptoms you experienced today.
 
7	
1. Did you take study medication yesterday? No  Yes 
 
If yes:
 
2. Did you experience muscle symptoms today? No  Yes  If yes:
 
3: Please indicate severity of muscle symptoms you experienced today.
 

Appendix 8: Summary of Product Characteristics for Atorvastatin 20 mg tablets

1 NAME OF THE MEDICINAL PRODUCT

Atorvastatin 20 mg Film-coated Tablets

2 QUALITATIVE AND QUANTITATIVE COMPOSITION

Each film coated tablet contains 20 mg atorvastatin (as atorvastatin calcium)

For a full list of excipients, see section 6.1.

3 PHARMACEUTICAL FORM

Film-coated tablet.

White to off-white, elliptic, biconvex and smooth film-coated tablets. The dimensions of each tablet are approximately 12.5 mm x 6.6 mm.

4 CLINICAL PARTICULARS

4.1 THERAPEUTIC INDICATIONS

Hypercholesterolaemia

Atorvastatin is indicated as an adjunct to diet for reduction of elevated total cholesterol (total-C), LDL-cholesterol (LDL-C), apolipoprotein B and triglycerides in adults, adolescents and children aged 10 years or older with primary hypercholesterolaemia including familial hypercholesterolaemia (heterozygous variant) or combined (mixed) hyperlipidaemia (corresponding to Types IIa and IIb of the Fredrickson classification) when response to diet and other non pharmacological measures is inadequate.

Atorvastatin is also indicated to reduce total-C and LDL-C in adults with homozygous familial hypercholesterolaemia as an adjunct to other lipid-lowering treatments (e.g. LDL apheresis) or if such treatments are unavailable.

Prevention of cardiovascular disease

Prevention of cardiovascular events in patients estimated to have a high risk for a first cardiovascular event (see section 5.1), as an adjunct to correction of other risk factors.

4.2 POSOLOGY AND METHOD OF ADMINISTRATION

Posology

The patient should be placed on a standard cholesterol-lowering diet before receiving atorvastatin and should continue on this diet during treatment with atorvastatin.

The dose should be individualised according to baseline LDL-C levels, the goal of therapy, and patient response.

The usual starting dose is 10 mg once a day. Adjustment of dose should be made at intervals of 4 weeks or more. The maximum dose is 80 mg once a day.

Primary hypercholesterolaemia and combined (mixed) hyperlipidaemia The majority of patients are controlled with atorvastatin 10 mg once a day. A therapeutic response is evident within 2 weeks, and the maximum therapeutic response is usually achieved within 4 weeks. The response is maintained during chronic therapy.

Heterozygous familial hypercholesterolaemia

Patients should be started with atorvastatin 10 mg daily. Doses should be individualised and adjusted every 4 weeks to 40 mg daily. Thereafter, either the dose may be increased to a maximum of 80 mg daily or a bile acid sequestrant may be combined with 40 mg atorvastatin once daily.

Homozygous familial hypercholesterolaemia

Only limited data are available (see section 5.1).

The dose of atorvastatin in patients with homozygous familial hypercholesterolaemia is 10 to 80 mg daily (see section 5.1). Atorvastatin should be used as an adjunct to other lipid-lowering treatments (e.g. LDL apheresis) in these patients or if such treatments are unavailable.

Prevention of cardiovascular disease

In the primary prevention trials the dose was 10 mg/day. Higher dosages may be necessary in order to attain (LDL-) cholesterol levels according to current guidelines.

Renal impairment

No adjustment of dose is required (see section 4.4).

Hepatic impairment

Atorvastatin should be used with caution in patients with hepatic impairment (see sections 4.4 and 5.2). Atorvastatin is contraindicated in patients with active liver disease (see section 4.3).

Use in the elderly

Efficacy and safety in patients older than 70 using recommended doses are similar to those seen in the general population.

Paediatric use

Hypercholesterolaemia:

Paediatric use should only be carried out by physicians experienced in the treatment of paediatric hyperlipidaemia and patients should be re-evaluated on a regular basis to assess progress.

For patients aged 10 years and above, the recommended starting dose of atorvastatin is 10 mg per day with titration up to 20 mg per day. Titration should be conducted according to the individual response and tolerability in paediatric patients. Safety information for paediatric patients treated with doses above 20 mg, corresponding to about 0.5 mg/kg, is limited.

There is limited experience in children between 6-10 years of age (see section 5.1). Atorvastatin is not indicated in the treatment of patients below the age of 10 years.

Other pharmaceutical forms/strengths may be more appropriate for this population.

Method of administration

Atorvastatin is for oral administration. Each daily dose of atorvastatin is given all at once and may be given at any time of day with or without food.

